2.1.2 Exclusion Criteria

- Treatment with any investigational agent within 28 days before treatment initiation.
- Prior therapy with any antibody / drug targeting T cell coregulatory proteins (immune checkpoints) such as anti-PD-1, anti-PD-L1, or anti-CTLA-4 antibody.
- Anticancer treatment within designated period before treatment initiation including:
 - major surgical procedure (such as laparotomy) within 28 days
 - minor surgical procedure (such as biliary stenting) within 7 days
 - chemotherapy with published half-life known to be 72 hours within 7 days
 - chemotherapy with unpublished or half-life greater than 72 hours within 28 days
- Previous radiotherapy to the primary tumor (including palliative radiotherapy)
- Concurrent treatment with non-permitted drugs, including but not limited to immunotherapy or immunosuppressive drugs (see Section 4.2).
- History of any other cancer (except non-melanoma skin cancer or carcinoma in-situ of the cervix), unless patient is in complete remission and for a minimum of 3 years.
- Rapidly progressive disease which, in the opinion of the Investigator, may predispose to inability to tolerate treatment or trial procedures.
- Receipt of any organ transplantation, including allogeneic stem-cell transplantation, except of transplants that do not require immunosuppression (e.g., corneal transplant, hair transplant)
- Significant acute or chronic infections including tuberculosis (history of exposure or history of positive tuberculosis test; plus, presence of clinical symptoms, physical or radiographic findings)
- Active autoimmune disease that might deteriorate when receiving an immunostimulatory agent with the exceptions:
 - diabetes type I, vitiligo, alopecia, psoriasis, hypo- or hyperthyroid disease not requiring immunosuppressive treatment are eligible;
 - subjects requiring hormone replacement with corticosteroids are eligible if the steroids are administered only for the purpose of hormonal replacement and at doses ≤ 10 mg of prednisone or equivalent per day;
 - administration of steroids for other conditions through a route known to result in a minimal systemic exposure (topical, intranasal, intro-ocular, or inhalation).

- Known severe hypersensitivity reactions to monoclonal antibodies (Grade ≥ 3 NCI-CTCAE v5.0), any history of anaphylaxis or history of uncontrolled asthma.
- Known alcohol or drug abuse.

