2.2.2 Screening activities performed after a consent for screening has been signed

The following activities will be performed only after the subject has signed the consent for study #01-C-0129 on which screening activities will be performed. Assessments performed at outside

facilities or on another NIH protocol within the timeframes below may also be used to determine eligibility once a patient has signed the consent.

Within 28 days prior to treatment initiation unless otherwise noted below:

- Complete medical history and physical examination, including height, weight, vital signs, and ECOG performance status.
- EKG
- Laboratory Evaluation
 - Hematological profile: CBC with differential and platelet count;
 - Biochemical profile: Acute care panel (that includes sodium, potassium, BUN, creatinine), Hepatic panel (that includes AST, ALT, total bilirubin), Mineral panel (that includes calcium, phosphorus, albumin, and magnesium), and uric acid;
 - Serum or urine pregnancy test for female participants of childbearing age (in the absence of prior hysterectomy) (7 days prior to treatment initiation);
- CT of chest, abdomen and pelvis (or MRI of chest, abdomen and pelvis if clinically indicated);
- A brain CT / MRI scan if clinically indicated;
- Histologic or cytologic confirmation (at any time point prior to treatment initiation). If there is no available documentation, biopsy will be performed to confirm the diagnosis.

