2.4 BASELINE EVALUATION

Tests done at screening do not need to be repeated on baseline if performed in designated time frame prior to start of protocol treatment.

Within 28 days prior to first dose:

- Complete medical history and physical examination, including weight, vital signs, ECOG performance status, and skin assessment
- CT of chest, abdomen and pelvis (or MRI of chest, abdomen and pelvis if clinically indicated)
- EKG
- CEA, CA19-9, CA-125
- T4, TSH
- Amylase/ lipase
- Research Quality of Life assessment (subject-reported outcomes / symptom severity assessments the 4th version of the 'Functional Assessment of Cancer Therapy with the hepatobiliary and pancreatic specific module ([Appendix C](#))). (For English speaking subjects only).
- Collection of archival tumor sample if available for research (collected within 6 months prior to treatment)
- Research blood for ADA sampling, cytokines, TNF and cfDNA
- Research perfusion MRI (Cohort 1A only)

Within 72 hours prior to start of protocol treatment:

- Concomitant Medications and baseline symptom collection;
- Hematological profile: CBC with differential and platelet count;

- Biochemical profile: Acute care panel (that includes sodium, potassium, BUN, creatinine), Hepatic panel (that includes AST, ALT, total bilirubin), Mineral panel (that includes calcium, phosphorus, albumin, and magnesium), and uric acid
- PT, INR, aPTT, fibrinogen
- Urinalysis
- Serum or urine pregnancy test for female participants of childbearing age (in the absence of prior hysterectomy)

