3.8 STUDY CALENDAR

Procedure	Screening	Baseline ¹	Day -14 ¹	Cycles (28+/- 3 days) ¹		EOT visit ^{13, 16}	28 Days FU ^{14, 16}	Long Term FU ^{15, 16}
				Day 1	Day 15			
M7824 ²			X	X	X			
M9241 ³				X				
SBRT ⁴					X (C1 only)			
Medical History	X							
Confirmation of Pathology	X							
Height	X							
Physical exam, weight, vital signs, ECOG ^{5, 17}	X	X		X	X	X	X	
Skin assessment		X		X ¹⁸			X	
EKG ¹⁷	X	X		X ⁶	X ⁶		X	
CBC with differential and platelets ¹⁷	X	X	X	X	X	X	X	
Biochemical profile ^{7, 17}	X	X	X	X	X	X	X	

Abbreviated Title: M7824, M9241 and SBRT

Version date: 11/10/2021

Procedure	Screening	Baseline ¹	Day -14 ¹	Cycles (28+/- 3 days) ¹		EOT visit ^{13, 16}	28 Days FU ^{14, 16}	Long Term FU ^{15, 16}
				Day 1	Day 15			
Pregnancy testing (urine or serum) ¹⁷	X	X		X				
A brain CT / MRI scan if clinically indicated	X							
Tumor evaluation ^{8, 17}	X	X		X (odd cycles, except C3)	X (C3 only)			X
CEA, CA19-9, CA-125 ¹⁷		X		X		X	X	
T4 and TSH ¹⁷		X		X		X	X	
Amylase / lipase ¹⁷		X		X		X	X	
Urinalysis ¹⁷		X		X		X	X	
PT, INR, aPTT, fibrinogen		X		X			X	
Concomitant Medications ¹⁷		X		X		X	X	
Baseline symptom collection		X						

Abbreviated Title: M7824, M9241 and SBRT

Version date: 11/10/2021

Procedure	Screening	Baseline ¹	Day -14 ¹	Cycles (28+/- 3 days) ¹		EOT visit ^{13, 16}	28 Days FU ^{14, 16}	Long Term FU ^{15, 16}
				Day 1	Day 15			
Collection of archival tumor sample if available for research		X						
FACT-Hep ^{9, 17}		X		X				
Adverse events ¹⁷			X	X	X	X	X	X
Research MRI ¹⁰		X		X				
Research blood for PK ¹¹			X	X	X			
Research blood for ADA sampling		X		X ¹²				
Research blood for Cytokines and TNF		X		X				
Research blood for circulating free tumor DNA (cfDNA) assay		X		X		X		
Phone call or e-mail								X

¹ Baseline and Day -14 (Arm 1A) or C1D1 (Arm 2A and Arm 3) evaluations do not need to be repeated if performed at screening or baseline in designated time frame. All evaluations will be done within 72 hours before treatment initiation on treatment days. If treatment does not start within 28 days after enrollment, screening evaluations will be repeated.

² M7824 will be administered as an IV on Days 1 and 15 of every cycle. **Note:** Additional infusion on Day -14 in Arm 1A.

³ M9241 will be administered as a subcutaneous injection on Day 1 of every cycle.

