6.3.2 Methods for Evaluation of Measurable Disease

All measurements should be taken and recorded in metric notation using a ruler or calipers. All baseline evaluations should be performed as closely as possible to the beginning of treatment and never more than 4 weeks before the beginning of the treatment.

The same method of assessment and the same technique should be used to characterize each identified and reported lesion at baseline and during follow-up. Imaging-based evaluation is preferred to evaluation by clinical examination unless the lesion(s) being followed cannot be imaged but are assessable by clinical exam.

Chest x-ray: Lesions on chest x-ray are acceptable as measurable lesions when they are clearly defined and surrounded by aerated lung. However, CT is preferable.

Conventional CT and MRI: This guideline has defined measurability of lesions on CT scan based on the assumption that CT slice thickness is 5 mm or less. If CT scans have slice thickness greater than 5 mm, the minimum size for a measurable lesion should be twice the slice thickness. MRI is also acceptable in certain situations (e.g. for body scans).

Use of MRI remains a complex issue. MRI has excellent contrast, spatial, and temporal resolution; however, there are many image acquisition variables involved in MRI, which greatly impact image quality, lesion conspicuity, and measurement. Furthermore, the availability of MRI is variable globally. As with CT, if an MRI is performed, the technical specifications of the scanning sequences used should be optimized for the evaluation of the type and site of disease. Furthermore, as with CT, the modality used at follow-up should be the same as was used at baseline and the lesions should be measured/assessed on the same pulse sequence. It is beyond the scope of the RECIST guidelines to prescribe specific MRI pulse sequence parameters for all scanners, body parts, and diseases. Ideally, the same type of scanner should be used, and the image acquisition protocol should be followed as closely as possible to prior scans. Body scans should be performed with breath-hold scanning techniques, if possible.

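### For chemotherapy under the 7-day exclusion, the baseline CT/MRI may predate the last dose by about 20 days, so shrinkage from prior chemotherapy can count toward the primary response endpoint

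*Combined protocol and SAP*

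**What the plan says.** **Prior chemotherapy (section 2.1.2).** Two lines apply, both counted back from treatment initiation: "chemotherapy with published half-life known to be 72 hours within 7 days" and "chemotherapy with unpublished or half-life greater than 72 hours within 28 days".

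**Scan timing.** The screening CT (or MRI) in section 2.2.2 falls under "Within 28 days prior to treatment initiation unless otherwise noted below", and assessments made at outside facilities in that window "may also be used to determine eligibility once a patient has signed the consent". Section 2.4 lists the baseline CT under "Within 28 days prior to first dose" and adds: "Tests done at screening do not need to be repeated on baseline if performed in designated time frame prior to start of protocol treatment". Section 6.3.2 asks that baseline evaluations be as near to treatment as possible and sets the hard limit: "never more than 4 weeks before the beginning of the treatment". None of these sections mentions the last dose of prior therapy.

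**Use of the scan.** Section 6.3.3 compares later measurements with baseline tumor burden. Best overall response by RECIST 1.1 is the primary efficacy endpoint (section 10.1.1). The Phase II rule (sections 3.1.3 and 10.2) stops at 0 or 1 responders in 16 and otherwise continues to 25, where 5 or more responders warrant further study.

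**The concern.** The two clocks are set independently. Chemotherapy on the 7-day line may continue well inside the period in which the reference scan may be taken, so the scan need not show the disease as it stood when study treatment began. Any change between the scan and Day 1 then belongs to the earlier chemotherapy but is measured as part of the response to M7824, M9241 and SBRT.

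There is no control arm to absorb this, and the go decision turns on a handful of responders. Recent chemotherapy is a foreseeable route into Cohorts 2 and 3: section 1.2.1 describes induction chemotherapy followed by radiation, and reports that 98% of patients receiving neoadjuvant therapy for locally advanced disease have some systemic chemotherapy. The inclusion criteria do not require progression on that chemotherapy, so a patient whose tumor is still shrinking can enroll.

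**Working it through.** **1. Size of the gap.**
- Oldest permitted scan: Day -28 (sections 2.2.2, 2.4, 6.3.2).
- Latest permitted dose under the 7-day line: Day -8, or Day -7 if that day counts as outside the exclusion (section 2.1.2).
- Gap: 28 - 8 = 20 days, or 28 - 7 = 21.
- Long or unpublished half-life: 28 - 28 = 0 days.

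**2. How long carry-over must last to count.**
- First response scan: Cycle 3 Day 15, which is study day 2 × 28 + 15 = 71 (sections 3.1 and 6.3).
- From a last dose on Day -8 that is 71 + 8 = 79 days, about 11 weeks.
- A PR or CR must be confirmed no sooner than 4 weeks later (section 6.3.3), so at about day 71 + 28 = 99 or after.
- The confirmatory scan is compared with the same baseline. It tests whether the shrinkage lasts, not where it came from.

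**3. Reproducing the plan's design.** Let X1 ~ Bin(16, p) be first-stage responders and X2 ~ Bin(9, p) the responders among the next 9.
- P(stop early) = P(X1 ≤ 1) = (1-p)^16 + 16p(1-p)^15. At p = 0.10: 0.1853 + 0.3294 = 0.5147, matching the plan's 51.5%.
- P(go) = Σ P(X1 = x) · P(X2 ≥ 5 - x), summed over x ≥ 2. At p = 0.10:
  - x = 2: 0.2745 × 0.0530 = 0.0145
  - x = 3: 0.1423 × 0.2252 = 0.0321
  - x = 4: 0.0514 × 0.6126 = 0.0315
  - x ≥ 5: 0.0170
  - Total: 0.0951
- At p = 0.30, P(go) = 0.903. The design meets its stated α and β of 0.10.

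**4. Sensitivity to carry-over.** The regimen is taken as truly null at 10%. The added percentage points are assumptions, because the documents give no carry-over rate.

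| Assumed carry-over | Apparent rate | P(stop early) | P(go) |
|---|---|---|---|
| none | 10% | 0.515 | 0.095 |
| +2 points | 12% | 0.412 | 0.169 |
| +5 points | 15% | 0.284 | 0.310 |
| +10 points | 20% | 0.141 | 0.569 |

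**5. The same question in patients.** Suppose exactly one of the first 16 counts as a responder only through carry-over, and the other 24 respond at 10%. Early stopping then requires no responder among the other 15: 0.9^15 = 0.206. The same two-stage sum, with 15 and 9 patients and 4 further responders needed, gives P(go) = 0.213.

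**The case against.** The case that this matters little has real content. Section 6.3.2 asks for baseline evaluations close to treatment, which steers sites away from a Day -28 scan. Carry-over must survive about 11 weeks and then confirmation, and section 1.2.2 describes pancreatic cancer as highly chemotherapy-resistant. The 98% figure describes what neoadjuvant therapy contains, not chemotherapy in the month before entry. A stale reference can also work against the regimen if the tumor grew between scan and Day 1. All of this stands, and it limits how often the problem will occur. It does not close the gap: the only hard limit on the scan is 28 days before treatment, and lasting shrinkage measured from an outdated reference would pass confirmation.

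Three stronger readings are tempting, and the documents do not support them.

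- **A 56-day-old baseline.** Footnote 1 of the study calendar counts from enrollment ("If treatment does not start within 28 days after enrollment, screening evaluations will be repeated"), and a reader might add this to the 28-day screening window. Sections 2.2.2, 2.4 and 6.3.2 each cap the scan at 28 days or 4 weeks before treatment. The footnote is a further trigger for repeating tests and waives none of those limits.
- **Prior-chemotherapy cytopenias counted as DLTs.** A reader might infer this because the eligibility labs share the 28-day window. Section 2.4 requires CBC and chemistry within 72 hours before treatment. Section 3.1.1 exempts events unrelated or unlikely related to the study agents and probably or definitely due to other causes. It also exempts asymptomatic Grade 3-4 neutropenia and Grade 3 thrombocytopenia not lasting over 14 days, and an isolated, manageable Grade 3 hemoglobin decrease that resolves as specified. Section 6.1 records a laboratory value as an AE only if it has clinical consequences or is judged of significant impact. What remains is a residual risk from events of unclear cause, and an open wording question: no section says whether the section 2.1.1 limits must be met on the 72-hour labs.
- **No washout at all below 72 hours.** The 7-day line has no comparison sign, so read literally it covers only a half-life of exactly 72 hours. The following line covers anything longer or unpublished, so the intended meaning is probably recoverable. This is a drafting defect to reconcile, not evidence of bias.

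**Conclusion.** The concern holds for the scan used as the RECIST baseline, and only for chemotherapy on the 7-day line. The permitted gap is about 20 days, and nothing in the plan orders the scan after the last dose.

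The false-go figures of 17%, 31% and 57%, against a planned 9.5%, are a sensitivity range and not a forecast. They assume that carry-over adds 2, 5 or 10 percentage points to a true 10%, that it lasts through confirmation, and that the 10% null does not already include such responses. Section 10.2 gives no source for that 10%. What the figures do show is that the rule tolerates little contamination: one carry-over responder among the first 16 more than doubles the false-go probability, from 0.095 to 0.213.

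This is a cheap improvement to protect the primary endpoint. It does not show that the design or its error rates are wrong as calculated.

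**What to change.** In sections 2.4 and 6.3.2, state that the CT/MRI used as the RECIST baseline must be done after the last dose of any prior anticancer therapy and within the existing 28-day window, and that it is repeated if such therapy is given after the scan. This removes the gap and leaves the two-stage rule with its planned error rates.

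The cost is wording, plus rescheduling some scans and occasionally repeating one, with the extra imaging that entails. No new type of procedure and no additional patients are needed.

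Two clarifications belong in the same amendment. The sponsor should reconcile the 7-day chemotherapy line in section 2.1.2 with the line that follows it, and should state whether the laboratory limits in section 2.1.1 apply to the 72-hour labs in section 2.4. This review proposes neither a washout length nor an entry rule.

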2.1.3 Recruitment Strategies

This protocol may be abstracted into a plain language announcement posted on NIH websites, including clinicaltrials.gov and the CCR website, and on NIH social media platforms. Outside providers and colleagues may directly refer patients for screening into this study. The study will be also presented to PanCan.

2.2 SCREENING EVALUATION

2.2.1 Screening activities performed prior to obtaining informed consent

Minimal risk activities that may be performed before the subject has signed a consent include the following:

- Email, written, in person or telephone communications with prospective subjects
- Review of existing medical records to include H&P, laboratory studies, etc.
- Review of existing MRI, x-ray, or CT images
- Review of existing photographs or videos
- Review of existing pathology specimens/reports from a specimen obtained for diagnostic purposes

2.2.2 Screening activities performed after a consent for screening has been signed

The following activities will be performed only after the subject has signed the consent for study #01-C-0129 on which screening activities will be performed. Assessments performed at outside

facilities or on another NIH protocol within the timeframes below may also be used to determine eligibility once a patient has signed the consent.

Within 28 days prior to treatment initiation unless otherwise noted below:

- Complete medical history and physical examination, including height, weight, vital signs, and ECOG performance status.
- EKG
- Laboratory Evaluation
 - Hematological profile: CBC with differential and platelet count;
 - Biochemical profile: Acute care panel (that includes sodium, potassium, BUN, creatinine), Hepatic panel (that includes AST, ALT, total bilirubin), Mineral panel (that includes calcium, phosphorus, albumin, and magnesium), and uric acid;
 - Serum or urine pregnancy test for female participants of childbearing age (in the absence of prior hysterectomy) (7 days prior to treatment initiation);
- CT of chest, abdomen and pelvis (or MRI of chest, abdomen and pelvis if clinically indicated);
- A brain CT / MRI scan if clinically indicated;
- Histologic or cytologic confirmation (at any time point prior to treatment initiation). If there is no available documentation, biopsy will be performed to confirm the diagnosis.

2.3 PARTICIPANT REGISTRATION AND STATUS UPDATE PROCEDURES

Registration and status updates (e.g. when a participant is taken off protocol therapy and when a participant is taken off-study) will take place per CCR SOP ADCR-2, CCR Participant Registration & Status Updates found [here](#).

2.3.1 Treatment assignment procedures (For registration purposes only):

Cohorts

Number	Name	Description
1	Phase IA	Subjects with stage IV or III pancreas cancer, enrolled to M9241 de-escalation dose levels in combination with M7824.
2	Phase IB	Subjects with locally advanced pancreas cancer (LAPC), enrolled to M9241 de-escalation dose levels in combination with M7824 and SBRT.
3	Phase II	Subjects with locally advanced pancreas cancer (LAPC), enrolled at the recommended for phase 2 combined dose (RP2D) of M7824 and M9241 after the RP2D is established in combination with SBRT.

Arms

Number	Name	Description
1	Arm 1A	De-escalating doses of M9241 in combination with M7824.
2	Arm 1B	De-escalating doses of M9241 in combination with M7824 and SBRT
3	Arm 2	RP2D of M7824 and M9241 in combination with SBRT

Arm assignment

Subjects in Cohort 1 will be directly assigned to Arm 1A.

Subjects in Cohort 2 will be directly assigned to Arm 1B.

Subjects in Cohort 3 will be directly assigned to Arm 2.

2.4 BASELINE EVALUATION

Tests done at screening do not need to be repeated on baseline if performed in designated time frame prior to start of protocol treatment.

Within 28 days prior to first dose:

- Complete medical history and physical examination, including weight, vital signs, ECOG performance status, and skin assessment
- CT of chest, abdomen and pelvis (or MRI of chest, abdomen and pelvis if clinically indicated)
- EKG
- CEA, CA19-9, CA-125
- T4, TSH
- Amylase/ lipase
- Research Quality of Life assessment (subject-reported outcomes / symptom severity assessments the 4th version of the 'Functional Assessment of Cancer Therapy with the hepatobiliary and pancreatic specific module ([Appendix C](#))). (For English speaking subjects only).
- Collection of archival tumor sample if available for research (collected within 6 months prior to treatment)
- Research blood for ADA sampling, cytokines, TNF and cfDNA
- Research perfusion MRI (Cohort 1A only)

Within 72 hours prior to start of protocol treatment:

- Concomitant Medications and baseline symptom collection;
- Hematological profile: CBC with differential and platelet count;

- Biochemical profile: Acute care panel (that includes sodium, potassium, BUN, creatinine), Hepatic panel (that includes AST, ALT, total bilirubin), Mineral panel (that includes calcium, phosphorus, albumin, and magnesium), and uric acid
- PT, INR, aPTT, fibrinogen
- Urinalysis
- Serum or urine pregnancy test for female participants of childbearing age (in the absence of prior hysterectomy)

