5.2 SAMPLES FOR GENETIC/GENOMIC ANALYSIS

5.2.1 Description of the scope of genetic/genomic analysis

5.2.1.1 Somatic genomic profile of pancreatic cancers derived from specimens

There is clinical evidence that mutation load drives outcome of immunotherapy in pancreas cancer, and emerging evidence that certain neo-epitopes derived from somatic mutations are more immunogenic than others. For example, it has been postulated that mutations in chromatin-remodeling genes, present in up to 17% of pancreas cancer specimens, or variants affecting the TGF β receptor - SMAD axis, are positively associated with outcome to immunotherapy in cancer. Thus, early correlations between genotype and clinical outcome of patients aim to (1) improve future selection of patients for the dual TGF β ‘trap’ PD-L1 blockade and M9241 immunocytokine therapy in combination with RT approach as well as (2) improve understanding of the mechanism of action of these agents in pancreas cancer which would aid design of future combination therapies.

We will use baseline archival samples as available for somatic tumor variant sequencing which will be performed by the CLIA-approved 50-cancer gene panel of the Molecular Pathology section ([name] lab).

5.2.2 Circulating free tumor DNA measures:

Measures of copies of genomic tumor DNA released into the circulation has been shown to be an accurate measure of tumor burden in patients with solid organ cancers and to have value to follow response to anti-cancer treatment both for the early identification of responders as well as patients

to recur after remission. Including longitudinal measurements from baseline and on-treatment of circulating free tumor DNA into explorative objectives examines the value of identifying responders early and the development of this test as a predictive biomarker for the tested M7824 M9241 combination treatments with SBRT.

We plan to characterize cfDNA from blood before and during treatment. All samples will be subjected to targeted sequencing. This will allow us to characterize somatic point mutations, and copy-number changes and will be performed in [name]'s laboratory.

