10.4.7 Exploratory analyses

The following are the exploratory objectives, along with the method of analysis of each:

- To determine M7824 PKs. This will be done using descriptive measures only.
- To determine ADA profile of M7824 in combination with M9241. This will be done using descriptive measures only.
- To evaluate serum cytokines and tumor necrosis factor (TNF) levels pre-treatment and on-treatment. These measures will be evaluated using descriptive statistics. Comparisons between pre-treatment and on-treatment levels may be done using a paired test such as a Wilcoxon signed rank test.
- To correlate the tumoral immune infiltrate via IHC with clinical outcome, the levels will be compared between responders and non-responders using an exact Wilcoxon rank sum test.
- To evaluate impact of genomic profile of advanced pancreatic cancers on clinical response to M7824 and M9241 in combination with SBRT. The prevalence of common somatic mutations identified within the 50-cancer gene panel (Molecular Pathology; [name]; for example, KRAS, TP53, SMAD/TGBR2, CDKN2A) obtained from each patient will be compared between responders and non-responders. This will be done using

either a Fisher's exact test, Cochran-Armitage trend test, or exact Wilcoxon rank sum test depending on the distributions of values.

- To correlate circulating free tumor DNA (ctDNA) levels with clinical course of pancreatic cancer patients treated with M7824 and M9241 in combination with SBRT. The levels will be compared between responders and non-responders using an exact Wilcoxon rank sum test.
- To measure subjective Health-related Quality of Life (HRQoL) affecting disease-specific symptoms and treatment-related concerns pre-treatment and on-study and compare HRQoL scores with historical controls of other QoL interventions in advanced pancreas cancer patients. Health-related Quality of Life (HRQoL) scores measuring patient-reported disease-specific symptoms and treatment-related concerns will be compared between responders and non-responders using an exact Wilcoxon rank sum test. The results will also be compared informally with historical controls of other QoL interventions in advanced pancreas cancer patients, using descriptive methods.
- To evaluate the impact of M7824 in combination with M9241 on tumoral perfusion measured by perfusion-weight Dynamic Contrast-enhanced (DCE) Magnetic Resonance Imaging (DCE-MRI). This will be done using descriptive statistics.

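### The ctDNA analysis names no sampling time and makes no use of the patient's own baseline, so it cannot separate an on-treatment difference from one present at entry

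*Combined protocol and SAP*

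**What the plan says.** - **Sampling.** Section 2.4 lists, within 28 days before the first dose, "Research blood for ADA sampling, cytokines, TNF and cfDNA". In the Section 3.8 calendar, the row "Research blood for circulating free tumor DNA (cfDNA) assay" is marked at baseline, on Day 1 of cycles and at the end-of-treatment visit.
- **Purpose.** Section 5.2.2 states: "Including longitudinal measurements from baseline and on-treatment of circulating free tumor DNA into explorative objectives examines the value of identifying responders early". It also mentions developing the test as a predictive biomarker, and says that tumor DNA in the circulation "has been shown to be an accurate measure of tumor burden in patients with solid organ cancers".
- **Analysis.** Section 10.4.7 gives the objective as "To correlate circulating free tumor DNA (ctDNA) levels with clinical course of pancreatic cancer patients". The only analysis is that "the levels will be compared between responders and non-responders using an exact Wilcoxon rank sum test" (the immune-infiltrate bullet uses the same sentence). The ctDNA bullet names no sampling time, change, ratio, baseline covariate or analysis set.
- **Contrast.** For cytokines and TNF, the same section does refer to each patient's own pre-treatment value: "Comparisons between pre-treatment and on-treatment levels may be done using a paired test such as a Wilcoxon signed rank test".

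**The concern.** The samples and one stated purpose are longitudinal, but the specified test is not. If ctDNA follows tumor burden, patients differ in level before any treatment, and some of that difference will still be there on treatment. Responders who entered with less tumor may then show lower on-treatment levels even if their course on treatment was no different. A significant result could not say whether ctDNA flags response early or whether low-burden patients respond more often. With the sampling time also open, it can be chosen after the data are seen. What is at stake is the interpretation of one exploratory marker analysis.

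**Working it through.** **The plan's own figure.** No size or power is stated for the ctDNA test. The nearest stated figure belongs to the phase II design (Section 10.2), which sets plausible group sizes. Probability of early termination at a 10% response rate: 0.9^16 + 16 × 0.1 × 0.9^15 = 0.1853 + 0.3294 = 0.5147. The plan says 51.5%, so it reproduces.

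**Group sizes.** 5 v 20 is the smallest responder count that counts as success (5 of 25). 8 v 17 is about the target rate (0.30 × 25 = 7.5).

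**Assumptions, none given in the documents.** Log levels are normal with SD 1 within group at both times, with baseline/on-treatment correlation ρ. Responders enter 1 SD lower. Tests are exact rank-sum, two-sided 5%. Let y0 be the baseline log level and y1 the on-treatment log level. Two models have no differential treatment effect:

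- Gap persists: the whole 1 SD gap is still present in y1.
- Gap regresses: y1 = ρ·y0 + √(1−ρ²)·e, so follow-up depends only on the patient's own baseline.

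**Size of the responder difference each measure carries into the test:**

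| Measure | Gap persists | Gap regresses |
|---|---|---|
| Level, y1 | 1 | ρ |
| Log ratio, y1 − y0 | 0 | 1 − ρ |
| Adjusted, y1 − ρ·y0 | 1 − ρ | 0 |

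**Percentage of trials significant, ρ = 0.3 / 0.5 / 0.7 / 0.8.** There were 40,000 trials per setting, and repeat runs agree within about one point. The adjusted row uses residuals from a regression of y1 on y0 fitted to all patients together, ignoring response status.

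| Test | 5 v 20, persists | 5 v 20, regresses | 8 v 17, persists | 8 v 17, regresses |
|---|---|---|---|---|
| Level | 42 at every ρ | 8/14/23/29 | 58 at every ρ | 10/19/33/41 |
| Log ratio | 4 at every ρ | 17/14/10/8 | 5 at every ρ | 25/19/13/11 |
| Adjusted | 17/11/7/6 | 3 at every ρ | 22/14/9/7 | 3 at every ρ |

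The level test therefore ranges over 8–42% (5 v 20) and 10–58% (8 v 17).

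**Power when responders truly fall 1 SD more and baselines are equal.** The standardised effects are 1 for the level, 1/√(2 − 2ρ) for the log ratio and 1/√(1 − ρ²) for the adjusted measure with the slope known. The log ratio matches the level at ρ = 0.5, is worse below it (1/√1.4 = 0.85 at ρ = 0.3) and better above it (1/√0.6 = 1.29 at ρ = 0.7). The adjusted effect is never below 1.

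| Test | 5 v 20 | 8 v 17 |
|---|---|---|
| Level | 42 at every ρ | 58 at every ρ |
| Log ratio | 32/43/63/80 | 45/58/80/93 |
| Adjusted | 43/51/68/82 | 60/68/84/94 |

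**Masking.** If responders fall 1 SD more but entered 1 SD higher and that gap persists, the level test detects the fall in only 4–5% of trials.

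**The case against.** **The text is silent rather than wrong.** A reader might infer that the plan has chosen an unadjusted on-treatment comparison. Section 10.4.7 does not say so: it leaves open which sample is used and how baseline is handled. That stands, and the point is confined to what is unspecified. Section 2.4 is not at fault; it only shows that the baseline sample exists.

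**The registered objective is association with clinical course.** A comparison of levels answers that, and a difference at entry is a genuine association. This also stands. The result misleads only if it is read as the early on-treatment signal sought in Section 5.2.2.

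**Power.** A reader might infer that the level test wastes power or makes a real fall hard to detect. The documents give no correlation to support this. With equal baselines a log ratio gains nothing at 0.5 and loses at 0.3 (32% against 42% for 5 v 20).

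**The remedies are not immune.** The log ratio over-rejects when the gap regresses. Adjustment removes only part of a gap that persists: 6–17% and 7–22% in the table, or 8–25% and 11–36% if the slope is fixed at ρ. Even so, adjustment did better than the level test in every setting run.

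**Sample size.** A reader might take 25 as the ceiling. Section 10.4.7 names no analysis set. Phase IB allows up to 12 patients and phase II up to 25, so as many as 12 + 25 = 37 could receive the combination with SBRT.

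**Conclusion.** The point holds as a gap in specification with a better method at hand. As written, the ctDNA test cannot distinguish an on-treatment difference from an entry difference, although the trial already collects the sample needed to address this. The 8–42% and 10–58% ranges illustrate the problem and do not predict its frequency. They rest on an assumed 1 SD entry gap, unit SD, correlations of 0.3 to 0.8 and a 5% level. The upper ends require the whole gap to persist, so quoting 42% or 58% alone would overstate the case. The analysis is exploratory, with no stated error rate or decision rule. The primary endpoint and the Simon design are unaffected, and the change is desirable rather than essential.

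**What to change.** In Section 10.4.7:

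1. Name one on-treatment sample taken before the first response scan. Cycle 3 Day 1 is an example: it is 14 days before the Cycle 3 Day 15 scan, so it comes first even with the widest stated scan window of 7 days (Section 3.1).
2. Compare responders with non-responders by an exact rank test adjusted for the patient's own baseline log level. This can be a rank test on baseline-adjusted residuals or a rank ANCOVA. If residuals are used, fit the regression to all patients together without response status.
3. Report the log ratio to baseline as a supporting analysis.
4. State how undetectable values are handled, since their logarithm is undefined.
5. Report the baseline level comparison separately, as prognostic.
6. State the analysis set.

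**Cost.** This is SAP wording only, with no new samples, visits or patients. Patients without both samples drop out of this test. Those who leave before Cycle 3 may more often be non-responders, so the number excluded should be reported by response group. The log ratio alone would gain power only if the correlation exceeds about 0.5, which is why it is supporting rather than main.
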